2.3 Randomization

Subjects will be entered into the interactive response technology (IRT) system at screening and assigned a subject number. At Visit 3 (baseline) randomization will be performed via the IRT system and treatment assigned in a 1:1 ratio to mirabegron or placebo. Prior to the initiation of the study treatment, on day 1, the site staff will contact the IRT system in order to determine the randomly assigned treatment. Subjects will be stratified by age category: 5 - <12 years and 12 - <18 years of age.

Subjects will be assigned a subject number at study entry (i.e., signing the ICF/assent). The subject numbers will be sequential and rising. The subject number will comprise of 10 digits; 5 digits for the site number (provided by the sponsor) and 5 digits for the consecutive subject number.

Subjects will be randomized to receive IP according to the randomization schedule obtained via the IRT system. The study site personnel will dispense the treatment according to the IRT system's assignment. Specific procedures for randomization through the IRT system are contained in the study procedures manual.

An enrolled subject who withdraws or discontinues before dosing or before randomization will be considered a screen failure. Randomized subjects who withdraw or discontinue will not be replaced.

3 SAMPLE SIZE

Efficacy of mirabegron in children will be based on both primary and secondary endpoints. Given the clinical hurdle to demonstrate efficacy in a population challenging to recruit, an alpha-level of 10% would appear reasonable and justified. In a study with propiverine in children, Marschall-Kehrel (2009) showed a difference in mean number of micturition episodes/24 hours of 0.8 between propiverine and placebo, with a standard deviation (SD) between 2.2 and 2.3. Assuming at least similar efficacy of mirabegron, with a treatment effect of 0.9 micturitions per day between mirabegron and placebo and a common SD of 2.3, a sample size of 82 evaluable subjects (children) per treatment group would provide a power of 80%.

These assumptions, together with levels for Type-1 error and power were agreed upon with Pediatric Committee in the current Pediatric Investigation Plan.

Under the assumption that after randomization about 10% of the subjects will not be evaluable for the analysis of the primary endpoint (i.e., not fulfilling the criteria for inclusion in FAS), at least 184 children (5 to < 12 years of age) must be randomized in order to have at least 164 evaluable children for the analysis of the primary efficacy endpoint. For adolescents, no formal sample size will be calculated, at least 32 adolescents (12 to <18 years of age) must be randomized, yielding at least 16 adolescents on mirabegron.

Further assuming a 50% screen failure rate, approximately 368 children have to be enrolled to achieve 184 children (5 to <12 years of age) randomized and approximately 64 adolescents will be enrolled to achieve at least 32 adolescents (12 to <18 years of age) randomized (at least 92 children and 16 adolescents must be randomized to mirabegron).

Recruitment will continue until the minimum number in both children and adolescents has been achieved.

4 ANALYSIS SETS

In accordance with International Conference on Harmonization (ICH) recommendations in guidelines E3 and E9, the following analysis sets will be used for the analyses.

The determination of whether subjects are included or excluded from the safety and efficacy analysis sets will be made prior to database hard-lock for the primary report and prior to unblinding.

4.1 All Screened Set

The All Screened Set consists of all subjects for whom a valid informed consent/assent is available, as per applicable local law.

Consent/assent should be obtained from the subject and his/her parent(s)/legal guardian(s), before start of pre-investigational period. Up to three signatures might be available from the informed consent/assent. For calculations using the date of informed consent/assent the last available date will be used.

The All Screened Set will be used to summarize disposition of subjects who were screened.

4.2 All Randomized Set

The All Randomized Set consists of all randomized subjects, i.e. all those subjects with a randomization number.

The All Randomized Set will be used to summarize disposition of subjects who were randomized to treatment.

4.3 Full Analysis Set

The Full Analysis Set (FAS) consists of all subjects who are randomized and receive at least 1 dose of IP and have at least 1 post baseline measurement for mean number of micturitions per 24 hours. The FAS will be analyzed by treatment arm as randomized (i.e., treatment arm based on randomization assignment).

This will be the primary analysis set for efficacy analyses. Selected demographic and baseline characteristics will also be summarized for the FAS.

4.4 Safety Analysis Set

The Safety Analysis Set (SAF) consists of all subjects who took at least 1 dose of IP. The safety set will be analyzed by treatment arm as treated (i.e., based on the treatment the subject actually received rather than the treatment to which the subject was randomized).

The SAF will be used for summaries of demographic and baseline characteristics and all safety- and tolerability-related variables.

4.5 Per Protocol Set

The Per Protocol Set (PPS) consists of all subjects who are randomized and receive at least 1 dose of IP and have at least 1 post baseline measurement for mean number of micturitions per 24 hours, and who do not meet criteria for PPS exclusion listed in Section 4.5.1 of this

SAP. Final judgments on exclusion of subjects from the PPS are to be made prior to data base hard lock and will be documented in the Classification Specification document.

The PPS will be used for sensitivity analyses of the efficacy data. Selected demographic and baseline characteristics may also be summarized for the PPS.

4.5.1 Reasons for Exclusion from Per Protocol Set

A subject may be excluded from the PPS if there has been a deviation from the protocol sufficient to affect the assessment of the efficacy of the study drug. Such deviations may include (but are not limited to) ineligible subjects being enrolled in the study, interventions performed that were prohibited by protocol, or when subjects did not adhere adequately to the study treatment or outcome assessments.

There will be no partial exclusion (e.g., of particular timepoints only) of a subject from the PPS; all of a subject's data will be excluded.

Some reasons for exclusion of a subject from the PPS are given below: however the decision on whether a particular protocol deviation (see Section 6.2.2) requires the exclusion of a subject will be confirmed at the Analysis Set Classification Meeting (ASCM) with all reasons for the decision documented in the meeting minutes.

Eligibility Deviations

The inclusion and exclusion criteria for the study are detailed in Sections 5.1 and 5.2 of the protocol. These are all assessed at Screening (Visit 1) and selected criteria are also assessed at baseline (Visit 3).

A subject will be excluded from the PPS if:

- Any of inclusion criteria 2 and 15 are not met
- Any of exclusion criteria 2, 4, 8, 10 and 28 are met

Violations of other inclusion and exclusion criteria may also result in exclusion of the PPS if it is considered that there is a risk that the violation affects the assessment of the efficacy of the study drug. All such violations will be considered on an individual basis at the ASCM.

Prohibited and restricted medications and non-drug therapies

A subject will be excluded from the PPS if they received prohibited medications or non-drug therapies. These include, but are not limited to, the following (see Table 12.6 in protocol for a more complete list):

- Anti-muscarinics (including tricyclic and tetracyclic antidepressants), desmopressin, alpha-blockers and prescribed or OTC drugs that are potent CYP3A4 inhibitors (e.g., ketoconazole). They have to be stopped at screening (Visit 1) as soon as informed consent/assent has been obtained and eligibility has been confirmed and are prohibited during the study
- A history of intravesical treatment with botulinum toxin within 9 months prior to screening (Visit 1) and intravesical administration of botulinum toxin during the study is prohibited

• A history of electrostimulation or bladder training within 2 weeks prior to screening (Visit 1) and at any time during the study (outside of study related urotherapy) is prohibited.

Administration of restricted medications will be assessed during medical review to determine if the usage has fallen outside the protocol restrictions and if there is a risk that baseline or endpoint measurements may be affected. A list of restricted medications is given in Appendix 12.6 of the protocol.

Compliance to study medication

A subject will be excluded from the PPS for any of the following reasons based on compliance to the study medication (see Section 5.5.2 for details on the calculation of the compliance rate between study visits and over the whole double-blind study period):

- Subject took double-blind study medication for less than 70 days.
- Compliance with the double-blind study medication during the entire double-blind treatment period is less than 70%.
- Compliance with the double-blind study medication has been assessed as being less than 80% between visit 6/week 8 and visit 7/week 12/EoT.

All evidence and reasons for determining a violation based on compliance to the study medication will be documented in the minutes of the ASCM.

Error in study drug administration

A subject will be excluded from the PPS if they were dispensed incorrectly allocated study medication at any time during the double-blind treatment period.

4.6 Pharmacokinetics Analysis Set

The Pharmacokinetic Analysis Set (PKAS) will consist of all subjects who took at least 1 dose of IP and contributed at least one pharmacokinetic sample in which the date and time of the sample and prior dose are known. Any formal definitions for exclusion of subjects or time points from the PKAS will be documented in the classification specifications and be determined at the classification meeting.

Since the actual bioanalytical results may only become available after the data review meeting, additional data points may be excluded at the time of pharmacokinetic analysis at the discretion of the GCMSL. These data points will be documented in the modeling report.

The PKAS is used for all tables and graphical summaries of the PK data.

4.7 Pharmacodynamic Analysis Set

Not applicable.

5 EFFICACY AND SAFETY ENDPOINTS

Data for the efficacy endpoints will be recorded on an e-diary. This e-diary consists of a:

- 5-day Weekday Diary (bladder diary, Monday Friday), which is used for a 5-day period to record micturition frequency and incontinence episodes, and
- 2-day Weekend Episodic Diary (Saturday and Sunday), which is used to record micturition frequency, incontinence episodes, (pee) volume measurements, and worst leakage severity.

A valid diary day for:

• "Volumes"

In the 2-day Weekend Episodic Diary, is any e-diary day for which at least one "Pee Volume" greater than 0 mL is recorded with complete date and time.

- "Micturitions"
- In 2-day Weekend Episodic Diary, is any diary day for which at least once "Pee Volume" greater than 0 is recorded.
- In 5-day Week Diary, is any diary day for which the response to the question "Number of times using the toilet during the day/night" is not missing.
 - "Incontinence episodes"
- In 2-day Weekend Episodic Diary, is any diary day for which at least:
 - One micturition ("Pee Volume" >0) and
 - One "Leakage" or "Pee in toilet and Leakage" are recorded.
- In 5-day Week Diary, is any diary day for which:
 - The response to the question "How was your day/night" is not missing.

A valid diary for an analysis visit is a diary with at least 4 valid diary days within that analysis visit window. If for more than 7 days the diary is filled in prior to a visit, only the last 7 days prior to that visit will be used for calculation of the efficacy endpoints.

The number of valid diary days: Count of the valid diary days during the 7-day diary period. Days of visits to the clinic will not be counted as valid diary days.

In the event that in the 2-day Weekend Episodic Diary there are two entries with the same collection date and time but with different times of entry on the device, the last entry (time) will be used for analysis.

For several of the secondary efficacy endpoints, diary data will be classified as either "daytime" or "nighttime", where "daytime" is considered to mean "between waking up in the morning and going to sleep later the same day or next day" and "nighttime" means "between going to sleep on a day and waking up on the same or next day".

Whether an entry into the 5-day Week Diary is done during daytime or nighttime is captured on this diary.

For entries into the 2-day Weekend Episodic Diary, "daytime" and "nighttime" will be derived from the time the subject went to sleep and the time the subject awakened. These times are entered on this diary by the subject.

The go-to-bed time for Sunday is not captured in the diary. In order to distinguish between daytime and nighttime on Sunday the go-to-sleep time will be imputed as occurring a short time after the second (evening) SBPM was performed: time of second SBPM plus 1 hour. If there is no time entered in the diary for the evening SBPM, then the go-to-sleep time will be imputed as 23:59 (on Sunday).

5.1 **Primary Efficacy Endpoint**

The primary efficacy endpoint is the change from baseline to week 12/EoT in mean number of micturitions per 24 hours in children (5 to <12 years of age).

Number of micturitions per 24 hours is calculated from:

• The response to the questions "Number of times using the toilet during the night" and "Number of times using the toilet during the day" on the 5-day Week Diary,

and

• The number of times a "Pee in toilet" or a "Pee in toilet and leakage" was entered into the 2-day Weekend Episodic Diary.

For a weekend day:

- The daytime micturitions will be derived from the number of times a "Pee in Toilet" or a "Pee in Toilet and Leakage" was entered into the 2-day Weekend Episodic Diary between the time the subject woke up (exclusive) and went to sleep (inclusive).
- The nighttime micturitions will be derived from the number of times a "Pee in Toilet" or a "Pee in Toilet and Leakage" was entered into the 2-day Weekend Episodic Diary between the time the subject went to sleep (exclusive) and woke up (inclusive).

The total number of micturitions per weekend day is equal to the total number of times, in the diary, an amount of pee was recorded during daytime and nighttime for that day.

For each subject, the mean number of micturitions at Visit x (x=4, 5, 6, 7), using all available (non-missing) number of micturitions per 24 hours for the valid days in the diary (at least 4 and maximally 7), will be calculated as:

Sum of the number of micturitions (per 24 hours) over the valid diary days prior to Visit x Number of valid diary days

Note:

- If for a week day (Monday Friday):
 - the number of daytime micturitions is missing but the number of nighttime micturitions is not missing then the number of micturitions for that day is considered to be the number of micturitions during the nighttime.

- the number of nighttime micturitions is missing but the number of daytime micturitions is not missing then the number of micturitions for that day is considered to be the number of micturitions during the daytime.
- both daytime and nighttime micturitions are missing then the number of micturitions for that day is considered missing.
 - If for a weekend day (Saturday Sunday):
- No pee volume is recorded for Saturday or for Sunday then the number of micturitions is missing for Saturday or Sunday, respectively.
- No pee volume is recorded for Saturday and for Sunday then the number of micturitions is missing for both days.

If the wake-up time is the same as the time of micturition, then the micturition will be counted as a nighttime micturition.

Note: the first micturition occurring at or after the time of wake-up is considered a nighttime micturition.

A micturition episode is counted as micturition regardless of whether volume voided was recorded or not.

A micturition will also be counted if the subject assessed an episode as both micturition and incontinence (leakage).

If data of more than 7 days prior to a visit is available, only the last 7 days prior to the visit will be used for the analysis.

The baseline will be defined by the micturitions results obtained from the diary 7 days prior to visit 3/week 0 (baseline).

The visit 7/week 12/EoT visit will be defined as the subject's value at week 12 or in case of missing week 12 data, the last available result post-baseline.

Subjects without baseline or any post-baseline value will not be included in the change from baseline calculation although they will be included in the summary for either baseline or any post-baseline visit whichever timepoint the data is available.

Change from baseline to visit 7/week 12/EoT is defined as:

Result at visit 7/week 12/EoT – Result at baseline (visit 3/week 0).

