5.2.3 Mean Number of Daytime Incontinence Episodes per 24 hours

For a week day the number of Incontinence Episodes per 24 hours will be derived from "Number of Leakages During the Day" and "Number of Leakages During the Night" of the 5-day Week Diary. Incontinence episodes on measuring days will be classified as daytime or nighttime episodes as entered in the 5-day Week Diary.

For a weekend day the number of incontinence episodes will be derived from the times a "Leakage" or a "Pee in Toilet and Leakage" was entered into the 2-day Weekend Episodic Diary. Whether an Incontinence Episode was during daytime or nighttime will be based on the time-points the subject went to sleep and woke-up.

For each subject, the mean number of incontinence episodes per day/night (during the day/night) at Visit x (x=4, 5, 6, and 7) will be calculated using all available (non-missing) number of incontinence episodes for the valid diary days in the 5-day Week Diary and in the 2-day Weekend Episodic Diary for daytime in the 7-day period before the visit:

Mean No. of Daytime Incontinence Episodes at Visit x =

Total number of "Daytime Leakage Counts" over the Valid Diary Days prior to Visit x Number of Valid Diary Days

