5.2.4 Mean Number of Daytime Micturitions per 24 hours

For a week day the daytime micturitions will be derived from "Number of Times using the Toilet During the Day" was entered into the 5-day Week Diary.

For a weekend day the daytime micturitions will be derived from the number of times a "Pee in Toilet" or a "Pee in Toilet and Leakage" was entered into the 2-day Weekend Episodic Diary between the time the subject woke-up (exclusive) and went to sleep (inclusive). However, the first micturition occurring at or after the time of wake-up it is considered a nighttime micturition, see Section 5.1.

The total number of micturitions per weekend day is equal to the total number of times, in the diary, an amount of pee was recorded during daytime for that day.

For each subject, the mean number of daytime micturitions at Visit x (x=4, 5, 6, and 7) in the week before the visit will be calculated as:

Sum of the Number of Daytime Micturitions (per day) over the Valid Diary Days prior to Visit x Number of Valid Diary Days

5.2.5 Number of Dry (incontinence free) Days per 7 Days at the End of the 12-weeks Treatment Period

For a week day a "Dry (incontinence free) Day" is defined as a day where the response is "Dry" to the question "How was your Day" and to "How was your Night".

Let D_{dry} be the number of valid diary days where the response to both questions was "Dry". Let D_{wet} be the number of valid diary days where the response to one of the two questions or to both questions was "Wet".

For a weekend day a "Dry (incontinence free) Day" is defined as a day where no "Leakage" and no "Pee in toilet and leakage" are reported. A "Wet (incontinence) Day" is defined as a day where a "Leakage" or a "Pee in toilet and leakage" is reported.

If $(D_{dry} + D_{wet}) > 3$, then the number of dry days per 7 days at Visit 7 will be calculated for a subject as:

 $\frac{D_{dry}}{(D_{dry}+D_{wet})} \times 7$, otherwise its value is missing.

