5.3.2 Improvement from Baseline in Worst Incontinence Grading

Worst Incontinence Grading is derived from:

- The response to "Worst Leakage during the Day" and "Worst Leakage during the Night" from the 5-day Week Diary, and is equal to the worst outcome from both daytime and nighttime responses during a diary day.
- The responses to "Worst Leakage Severity" every time it is reported in the 2-day Weekend Episodic Diary. The worst response to the questions given during a diary day will be used for analysis.

Possible outcomes are: Dry; Slightly Wet; Moderately Wet; and Fully Wet.

Dry will be derived from the question on the 5-day Week Diary: "How was your day/night", and from the 2-day Episodic Weekend Diary if no leakages are reported during a diary day.

For each subject and visit the worst incontinence grade will be determined as the worst grading over the valid diary days preceding the study visit.

Improvement:

For Visit x (x=3, 4, 5, 6 and 7) the average over the valid week and weekend diary days will be calculated from the score of what was the worst leakage during the day", *i.e.*, 0 - Dry, 1 - Slightly Wet; 2 - Moderately Wet; and 3 - Fully Wet:

Worst Incontinence Grade at Visit x =

```
Sum of Worst Incontinence Gradings over the Valid Diary Days prior to Visit x
Number of Valid Diary Days
```

For each subject, improvement at Visit x if:

Worst Incontinence Grade (Visit x) - Worst Incontinence Grade (Visit 3 [Baseline]) < 0.

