5.3.8 Mean Number of Incontinence Episodes per 24 hours (adolescents)

See Section 5.2.3.

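### SAP section 5 does not count a completed leak-free weekend day as valid for incontinence, so 5.2.3 overstates mean daytime incontinence for children who have such days

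*SAP*

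**What the plan says.** SAP section 5 sets separate valid-day rules for volumes, micturitions and incontinence. For incontinence in the 2-day weekend diary it requires at least one void with volume above 0 and, joined by 'and', at least "One 'Leakage' or 'Pee in toilet and Leakage' are recorded". In the 5-day weekday diary only the day/night question has to be answered, so a dry weekday is valid.

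Section 5.2.3 defines the mean as a fraction, printed here on one line with the last five words as its denominator: "Total number of 'Daytime Leakage Counts' over the Valid Diary Days prior to Visit x Number of Valid Diary Days". Section 5.3.8 (adolescents) gives no derivation of its own: "See Section 5.2.3".

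Two other sections treat a leak-free weekend day as dry. In 5.2.5 a dry weekend day is "defined as a day where no 'Leakage' and no 'Pee in toilet and leakage' are reported", although D_dry is said to "be the number of valid diary days where the response to both questions was" dry. Section 5.3.2 takes the Dry grade (score 0) "from the 2-day Episodic Weekend Diary if no leakages are reported during a diary day", but its average is built on the "Sum of Worst Incontinence Gradings over the Valid Diary Days prior to Visit x". Section 6.4.3 describes the same grade as averaged over seven days.

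Section 5 also sets a minimum: "A valid diary for an analysis visit is a diary with at least 4 valid diary days within that analysis visit window". It does not say which of the three kinds of valid day is counted.

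**The concern.** The weekend rule makes validity depend on the outcome. A completed weekend day with voids and no leak is discarded, while the same day with a leak is kept. On weekdays dry and wet days are both kept. Dryness is what treatment is meant to produce, so the rule removes favourable days from a named secondary endpoint in children.

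The rule also sits badly with 5.2.5 and 5.3.2, which call the same day dry. Two programmers working from different sections could produce different values. If the four-day minimum counts incontinence-valid days, whether a value is missing would also depend on leakage, and the LOCF analysis in 6.4.2 would then fill the gap.

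**Working it through.** The documents give no figure for this endpoint, so there is nothing to reproduce. The check applies the 5.2.3 formula under two rules: (a) section 5 as written; (b) a leak-free weekend day with a recorded void kept as 0 episodes.

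**Single child.** A dropped leak-free day removes 0 from the numerator and 1 from the denominator. With seven completed days, k leak-free weekend days and a total of L daytime leaks (L > 0), rule (a) gives L/(7−k) and rule (b) gives L/7. The ratio is 7/(7−k): 7/6 = 1.17 for k = 1 and 7/5 = 1.40 for k = 2. The ratio is 1 when both weekend days have a leak. When L = 0 both rules give 0. A weekend day with only a night-time leak stays valid and correctly adds 0 daytime leaks.

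**Change from baseline.** Baseline: one daytime leak on each of seven days, 7/7 = 1.00. Week 12: one leak on each weekday and a dry weekend.
- Rule (a): 5/5 − 7/7 = 0.
- Rule (b): 5/7 − 7/7 = −0.29.

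**Group mean (assumed rates).** The SAP gives no leak distribution. I assumed complete seven-day diaries, Poisson daytime leaks with gamma-distributed child rates (shape 1 or 2, mean 0.3 to 2 per day) and a night rate of 0, 0.25 or 0.5 of the day rate. Protocol inclusion criterion 16 puts the entry level at one or more daytime episodes per day; the lower rates represent response. Overstatement of the daytime mean, by numerical integration:

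| Shape, night ratio | 0.3/day | 1/day | 2/day |
|---|---|---|---|
| 1, 0 | 18.8% | 7.7% | 3.4% |
| 1, 0.25 | 16.7% | 6.0% | 2.5% |
| 1, 0.5 | 14.9% | 4.9% | 1.9% |
| 2, 0 | 21.0% | 9.1% | 3.8% |
| 2, 0.25 | 18.9% | 7.1% | 2.6% |
| 2, 0.5 | 17.1% | 5.6% | 1.9% |

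In absolute terms the overstatement is 0.038 to 0.091 episodes per day. The relative error is largest at low rates; the absolute error peaks at about 0.7 to 1 leak per day. A simulation of 1,000,000 children (shape 2, ratio 0.25, mean 1) gave +7.08%, equal to the integrated value.

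**Between arms.** For assumed pairs 0.6 v 0.3, 1.0 v 0.7, 1.5 v 1.0 and 2.0 v 1.5 per day, the difference in daytime means changed by −1.9% to +7.4% (−0.010 to +0.022 episodes per day); repeated simulation put it at about −2% to +7.5%.

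**Four-day minimum, if it counts incontinence-valid days.** With a leak-free weekend, two missed weekdays leave 5 − 2 = 3 < 4, so the value is missing. With leaks on both weekend days, three missed weekdays leave 7 − 3 = 4 (enough) and four leave 3 (missing).

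**5.2.5 and 5.3.2, only if the section 5 rule governs them.** In the example above, the 5.3.2 grade (1 on each wet day) would show 0 instead of −0.29, and dry days at week 12 would be 0 instead of 2. Over the same assumed grid, dry days would be understated by 0.20 to 0.44 per week.

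**The case against.** The strongest reply is that the intention is plain: 5.2.5 and 5.3.2 treat a leak-free weekend day as dry, so a programmer would score it 0 in 5.2.3 too. The intention may well be that, but 5.2.3 has no dry-day rule of its own to set against section 5. Scoring the day 0 there would depart from the written definition.

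A second reply is that an empty leak field in an episodic diary does not prove dryness, so asking for more evidence is prudent. There is something in this. But requiring a leak does not test completeness; it selects on the outcome.

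Third, the same rule applies in both arms, so the comparison hardly moves. That stands. A reader might infer that the treatment effect is biased in a known direction; the calculations show a small shift of either sign, on leak rates that are assumptions.

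A reader might also infer that the dry-day count and the worst grade are certainly wrong. The documents do not support that. The weekend definition in 5.2.5 carries no validity condition. Section 5.3.2 scores the day 0, and 6.4.3 speaks of a seven-day average. That is not decisive, because 6.4.3 lists only scores 1 to 3. Both endpoints are ambiguous rather than wrong.

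**Conclusion.** The section 5 weekend rule is wrong as written for 5.2.3 and should be corrected before database lock. It inflates the mean by exactly 7/6 or 7/5 for a child with seven completed days, one or two leak-free weekend days and a daytime leak on another valid day. Other children with complete diaries are unaffected. The group-level range of about 1.9% to 21% rests on the assumed leak model and on complete diaries.

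The consequence for inference is modest. The between-arm difference changes little, and 5.3.8 inherits the rule but is descriptive. It would be a mistake to extend the point to the primary endpoint: micturitions have their own valid-day rule, which needs no leak. The responder categories in 5.3.1 use a sum over seven days and have no such denominator. The effects on 5.2.5, on 5.3.2 and on missingness are conditional on readings that the SAP leaves open.

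**What to change.** In SAP section 5, define a weekend day as valid for incontinence by a condition that does not involve leakage. Choose one:
- at least one void entry (pee in toilet, or pee in toilet and leakage), whether or not a volume was recorded; or
- at least one pee volume above 0, to match the weekend micturition rule.

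Add that a valid day with no leakage entry counts as 0 episodes (dry). If the void-entry version is chosen, check it against 5.1, which sets weekend micturitions to missing when no volume is recorded. Do not add a leakage entry as an alternative route to validity: among days that fail the void or volume condition, that would again keep wet days and drop dry ones.

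State that 5.2.3, 5.2.5, 5.3.2 and 5.3.8 all use this definition and that the four-day minimum counts these days.

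The cost is two or three sentences and a derivation change before database lock, with no new data. There is a small downside: a sparsely completed weekend day with an unrecorded leak is counted as dry, which lowers the mean slightly. Sections 5.2.5 and 5.3.2 already imply this.
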